**H. Sustainability**

1. How can we sustain the giving of kits through ANC and PLWHIV?
2. How can the community help in sustaining the different ways of distributing the kits?
3. What are the factors in the community that may cause these ways of distribution to be unsuccessful?
4. What do you think can be done to motivate the distributors?
5. What do you think are the demotivating factors?
6. In conclusion, are there any recommendations that you would like to share?

Thank you very much for the time you have spent in answering these questions today. Please remember that this information is confidential.

## **FGD with Community Members (Community led models)**

Thank you for taking time to speak with me today. My name is \_\_\_\_\_ and I am working with Zambart. To increase the uptake of HIV services, HIV self – testing kits are being distributed in the community. We would like to hear what you think about this as well as what the community thinks. We will record the interview to make sure that we capture all the valuable information that you share with me. We will also be taking down notes so that I do not forget what we have discussed. Please feel free to give honest answers as what we say is confidential. We will not record your name on the tape or on the notes that will be written and no one else will see the tape or the notes besides people who are working on this research project.

### **A. Physical Factors**

1. What do you think of the place (refer to different collection points) where people collect the HIVST kit? (Probe: conducive, comfortable)
2. What do you think of the space where HIVST kit collection is being done? (Probe; appropriateness)
3. What do you think about the time of the distribution of kits? (Probe: is it ok, could it be changed, could you suggest the best time)

### **B. Community/Social factors and stigma**

1. What other testing services are available in this community?
2. How did the availability of other testing services other than HIVST affect people's decision?
3. How does the anticipation of what people may say after someone tests using HIVST influence the decision? What do you expect people to say?

### **C. Process of delivering the kit to the secondary recipient**

1. How do you feel about this program of distributing kits through (ANC, ART, Tuntemba, work place clinic?)
2. What do people say about collecting kits for their partner from (ANC, ART, Tuntemba, work place?)
3. In your opinion, how did women/men feel about being the ones to give their partner a kit? (Comfortable why, not comfortable why)
4. In your opinion, how did men/women feel about receiving a kit from their partner?
5. Why do you think people decided to collect the kit for their partners?
6. In your opinion, what are the advantages of collecting the kit for your partner?
7. What are the disadvantages of collecting the kit for your partner?
8. Describe how the process of giving kits to partners has been in the community

**D. Equity**

1. Who do you think is accessing these services (Collecting of kits and using them?)
2. Why are they accessing the service?
3. In your opinion, is there a group of people who want to access the service but are failing? (Why?)
4. In your opinion, what can the community do to help such people access the service?
5. In your opinion, what can the health workers do to help such people access the service?
6. Are certain groups of people accessing the kits more than the other?

**E. Linkage to care**

1. Do you think are people going for a confirmatory test? Can anyone share an experience (what influenced the decision, where was the test conducted if you have done it). Probe: trust of test kit, partner support,
2. How easy or difficult do you it is to have a confirmatory test done? Probe: availability of testing services, location of testing services, stigma, attitude of HCWs,
3. (For those who are negative) How easy or difficult was it to access prevention services- condoms, VMMC, PMTCT (for those who tested negative and are willing to share experience)
4. Do you know anyone who has started treatment as a result of secondary distribution?
  - a. (For those who have started treatment) What factors may have facilitated their decision to start treatment? Probe:
  - b. (For those who have not started treatment) What factors may have hindered their decision to start treatment? Probe:
5. In your opinion, what are the other barrier of linkage to confirmatory testing and care?
6. What can be done to help people who receive kits through their partner link to care?

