As this model will be embedded within the MOH existing work flows, there will be no formal remuneration of work done but non-monetary recognition will be given to highly performing departments and facilities. Data will be collected by facility lay counsellors and HCWs using provided registers. Passive individual tracking will be done and linkage rate to care, treatment will be established through facility level testing and immediate returning of kits for recording. In addition, Linkage rate to care, treatment established through PHIA and DHS. The audience for this model is all targeted population above the age of 16 years.

**Community-led:** The community-led model will use the existing community structures that are otherwise not directly linked to the health facilities.

- In the SFH sites, the distribution will be through shops that will act as community access points. The concept of using these community access points for distribution of HIV prevention products has been tried and proven successful within SFH programs, specifically under the SARAI family planning project where condoms are distributed from community shops at no cost to the client. Similarly, the community access points willing to distribute HIVST materials will be identified and trained to distribute HIVST kits to members of the community free of charge. Data will be collected by shop owners using simplified registers that will capture vital project information. There will be no formal remuneration of work done but non-monetary recognition will be given to highly performing outlets. In addition, shops will enjoy free radio advertisement that will be provided during radio HIVST demand creation programs. There will be no individual tracking for linkage to care and treatment, but this will be established through PHIA and demographic health surveys.
- In the non-SFH sites managed by Zambart, the process will involve identification of community hubs (such as kantembas) and training of the existing carder of lay counsellors called Community HIV providers (CHiPs) on how to support the kantembas in the distribution of HIVST services and linkage to the health facility. Data will be collected by the CHiPs using the electronic data capture devices. In these sites, the lay workers will actively track linkage to confirmatory and linkage to care particularly linkage to the community health facility.

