**F. Social harms**

1. Where there any unfavourable outcomes of giving the self - test kit to a partner by a partner? (Probe experiences gender-based violence, humiliation, stigma or discrimination)
2. How can such incidents be prevented?
3. How can they be detected?
4. Where can one report such incidents?
5. What can the community do to prevent such harms?

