**D. Linkage to care**

1. How easy or difficult do you think it is to have a confirmatory test done? Probe: availability of testing services, location of testing services, stigma, attitude of HCWs,
2. (For those who are negative) How easy or difficult was it to access prevention services- condoms, VMMC, PMTCT (for those who tested negative and are willing to share experience)
3. Do you know anyone who has started treatment as a result of kantemba/ community hub distribution?
  - a. **(For those who have started treatment)** What factors may have facilitated their decision to start treatment? Probe:
  - b. **(For those who have not started treatment)** What factors may have hindered their decision to start treatment? Probe:
4. In your opinion, what are the other barrier of linkage to confirmatory testing and care?
5. What can be done to help people who access kits through the community hubs link to care?
6. Do you have anything to add?

We have come to the end of our interview, thank you very much for your time.

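### The community-led focus-group guide keeps partner-only questions on kit delivery, treatment start and social harms, so it under-collects data on people who took a kit for themselves

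*Protocol*

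**What the plan says.** Appendix 1 of the Protocol (section 2, combined community- and facility-led model) describes direct supply. At the sites run by the Society for Family Health (SFH), shops are "trained to distribute HIVST kits to members of the community free of charge"; at the Zambart-managed sites, community hubs such as kantembas do the same job.

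Section 2.2 sets objectives 2 (experiences), 3 (contextual factors) and 4 (frequency and nature of social harms) for each of the five models. Section 5.1 gives two of the 12 focus groups to the facility-led/community-led model.

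The Appendix 4 guide titled FGD with Community Members (Community led models) contains:

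- Section C, headed "Process of delivering the kit to the secondary recipient", with questions such as "What do people say about collecting kits for their partner from (ANC, ART, Tuntemba, work place".
- Section E, item 4: "Do you know anyone who has started treatment as a result of secondary distribution".
- Section E, item 6: "What can be done to help people who receive kits through their partner link to care".
- Section F, item 1: "Where there any unfavourable outcomes of giving the self - test kit to a partner by a partner".

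The community-led interview guide in the same appendix (IDI for community led models, section D) words the counterpart of E6 for its own model: "What can be done to help people who access kits through the community hubs link to care". Its counterpart of E4 asks about treatment started through kantemba or community hub distribution.

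**The concern.** In this model a typical recipient walks up to a shop or kantemba and takes a kit. The guide's questions on how a kit is passed on, who started treatment and what went wrong all assume a kit handed from one partner to another. A participant who collected a kit for themselves, or knows someone who did, is not prompted on these topics.

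Section 7.1 plans to compare findings across themes, participants and distribution models. If a topic is asked about the partner route only, little said about direct takers under that theme may reflect the prompt and not the model. This matters most for harms. Neither of the two community-led user interview guides printed in Appendix 4 has a social-harms section, so section F of the focus-group guide is where this model's users and community members are asked about harms in a group or interview guide.

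**Working it through.** The Protocol gives no figure to reproduce. The check is a count of questions and a comparison of guides.

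**Step 1. Count of numbered questions in the community-led focus-group guide.** An item counts as partner-only if it names a partner or secondary distribution as the route, or refers back to such an item.

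| Section | Questions | Partner-only | Which |
|---|---|---|---|
| A Physical factors | 3 | 0 | |
| B Community factors, stigma | 3 | 0 | |
| C Delivery | 8 | 7 | C2–C8 |
| D Equity | 6 | 0 | |
| E Linkage | 6 | 2 | E4 (with 4a, 4b), E6 |
| F Social harms | 5 | 5 | F1; F2–F5 refer back to it |
| G Sustainability | 6 | 0 | |
| Total | 37 | 14 | |

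Explicitly partner-only: 7 + 2 + 1 = 10, and 10/37 = 27%. Adding the four dependent harms items: 10 + 4 = 14, and 14/37 = 38%. Remainder: 37 − 14 = 23, and 23/37 = 62%.

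**Step 2. Where the items came from.** In the secondary-distribution focus-group guide, section C asks nearly the same partner questions in the same order as C2–C8. Its section F has a treatment-start item that differs from E4 only in a connecting phrase, and a closing item that matches E6. Its harms section opens with the same question as F1. The most natural explanation is carry-over.

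**Step 3. What was adapted and what was not.** Section A now reads "What do you think of the place (refer to different collection points) where people collect the HIVST kit" where the secondary-distribution guide names the ANC and ART hub. C1 and C2 add tuntemba and the workplace, and G1 adds shops. E4, E6 and F1 were left on the partner route. The community-led interview guide changed both linkage items (section D, items 3 and 5), so suitable wording already exists in the Protocol.

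**Step 4. Groups affected.** Section 5.1 allocates 4 + 4 + 1 + 2 + 1 = 12 focus groups; 2 of the 12 belong to this model. At 8 to 12 people per group (section 4.2), that is 16 to 24 participants. The 8 groups for the ANC and HIV-positive models already cover partner delivery.

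**The case against.** The best reply is that partner questions belong here. Objective 3 covers direct and secondary recipients in every model. Section 4.2 says the focus groups will seek community views that include secondary distribution. Section 3 trains distributors to offer kits for that purpose, and section 10.2 foresees a man asking for a kit for his partner in other models. This stands: the partner items are in scope, and C2 asks about partner kits from tuntemba by name. What is missing is the direct route beside them.

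A reader might infer that these groups will describe the two secondary-distribution models instead of their own. The documents do not support that. Most questions (23 of 37) are neutral or name community outlets; A1–A3, C1 and D1 touch on collection, and E1–E3 and E5 ask about confirmatory testing, prevention and barriers without restricting the route.

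Nor are these the only group data, since section 4.2 also plans stakeholder discussions, community consultations and mapping. Nothing says the guide will be used for the VMMC or workplace groups, so no effect there can be claimed.

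Other tools also cover direct use: the community-led interviews, the distributor interview and the hub observation tool. This softens the gap on delivery and treatment start. It closes the harms gap less well: the distributor guide asks distributors for their views, and the community reporting mechanisms in section 5.1 record incidents; neither replaces users' accounts in discussion.

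Finally, a facilitator can improvise. But section 7.1 itself relies on scripted probes to produce detailed accounts, so the script should contain them.

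**Conclusion.** The point holds as a defect of one instrument. C2–C8, E4, E6 and F1–F5 ask only about kits passed between partners, while the model mainly supplies kits directly. The two focus groups allocated to it will under-collect data on obtaining a kit, starting treatment and harms among people who took one for themselves.

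The size is 14 of 37 questions in 2 of 12 groups. These 14 include the sole treatment-start item and the whole harms section. Sample size, power and the primary outcome of the quantitative cohorts are untouched. The study does describe its data collection as predominantly qualitative (section 2.3), which makes its guides core instruments and the correction worth making before the groups are held.

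The conclusion assumes that both groups use this guide, which its title implies, and that facilitators broadly follow it. It does not assume that answers about partner delivery would be miscoded; section 7.1 leaves room to code them as such.

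**What to change.** Edit the community-led focus-group guide as follows.

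- **Section C.** Change the heading to cover obtaining and passing on a kit. Reword C2–C8 so each asks about collecting a kit from the shop or kantemba for one's own use as well as for a partner. The partner content stays.
- **E4 and E6.** Adopt the wording of items 3 and 5 in section D of the community-led interview guide, and add a probe for kits received through a partner.
- **F1.** Ask about unfavourable outcomes of obtaining or using a kit by either route. F2–F5 then follow without change.

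The cost is a text edit to one guide and translation of the changed items into the two local languages named in section 8.1. No groups or participants are added.

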**F. Social harms**

1. Where there any unfavourable outcomes of giving the self - test kit to a partner by a partner? (Probe experiences gender-based violence, humiliation, stigma or discrimination)
2. How can such incidents be prevented?
3. How can they be detected?
4. Where can one report such incidents?
5. What can the community do to prevent such harms?

**G. Sustainability**

1. How can we sustain the giving of kits through ANC, PLWHIV, and Shops?
2. How can the community help in sustaining the different ways of distributing the kits?
3. What are the factors in the community that may cause these ways of distribution to be unsuccessful?
4. What do you think can be done to motivate the distributors?
5. What do you think are the demotivating factors?

6. In conclusion, are there any recommendations that you would like to share?

Thank you very much for the time you have spent in answering these questions today. Please remember that this information is confidential.

### **IDI for community led models**

Thank you for taking time to speak with me today. My name is \_\_\_\_\_ and I am working with Zambart. In order to increase the uptake of HIV services, HIV self – testing kits are being distributed in the community. We would like to hear what you think about this as well as what the community thinks. We will record the interview to make sure that we capture all the valuable information that you share with me. We will also be taking down notes so that I do not forget what we have discussed. Please feel free to give honest answers as what we say is confidential. We will not record your name on the tape or on the notes that will be written and no one else will see the tape or the notes besides people who are working on this research project.

#### **A. General information**

1. (record sex of participant)
2. What year were you born?
3. Where do you live- zone/ section of the community?
4. What is your marital status?
5. How far did you go in your education?
6. What is your religion?

#### **B. Knowledge of HIV/ HIVST and attitudes towards testing for HIV?**

1. What methods of HIV testing do you know?
2. What are the advantages and disadvantages of testing for HIV using this/ these method (s)?
3. How often do you test for HIV and why? It usually takes a long time/ a short time before you test, why? (probing for attitudes)
4. How often do you come to access HIV services and why?

#### **C. Location and lay-out of distribution points, including community social and physical features**

1. What do you like about the location of the kantemba/hub distribution point? (probe)
2. What didn't you like about the location of distribution kantemba/hub point? (probe)
3. How did the location improve or hinder your access of HIVST services? (probe)
4. How did the location influence your decision to accept or reject HIVST? (probe)
5. What could be done to improve this service?

**D. Linkage to care**

1. How easy or difficult do you think it is to have a confirmatory test done? Probe: availability of testing services, location of testing services, stigma, attitude of HCWs,
2. (For those who are negative) How easy or difficult was it to access prevention services- condoms, VMMC, PMTCT (for those who tested negative and are willing to share experience)
3. Do you know anyone who has started treatment as a result of kantemba/ community hub distribution?
  - a. **(For those who have started treatment)** What factors may have facilitated their decision to start treatment? Probe:
  - b. **(For those who have not started treatment)** What factors may have hindered their decision to start treatment? Probe:
4. In your opinion, what are the other barrier of linkage to confirmatory testing and care?
5. What can be done to help people who access kits through the community hubs link to care?
6. Do you have anything to add?

We have come to the end of our interview, thank you very much for your time.

### **IDI guide for health care workers**

Thank you for taking time to speak with me today. My name is \_\_\_\_\_ and I am working with Zambart a research organization. To increase the uptake of HIV services, HIV self – testing kits are being distributed at the ARTs clinic and ANC. We would like to hear what you think about this as well as what the community thinks. We will record the interview to make sure that we capture all the valuable information that you share with me. We will also be taking down notes so that I do not forget what we have discussed. Please feel free to give honest answers as what we say is confidential. We will not record your name on the tape or on the notes that will be written and no one else will see the tape or the notes besides people who are working on this research project.

#### **A. HIV-Self testing**

1. What is your understanding of HIV self-testing?
  - a. Definition
  - b. Procedures
    - i. Processes for sample collection, analysis, and interpretation of results
  - c. Do you feel you have good understanding of all aspects related to self-testing?
    - i. What is the source of your current knowledge on self-testing?
    - ii. In what instances are confirmatory tests required?
    - iii. What sort of information/training would you need to better support self-testing patients/participants?

#### **B. Evaluating the model**

1. What do you think about (community-based, ANC, PLWHIV, Tuntemba) distribution of HIV self-test kits?
  - a. Is it a good/bad thing? Please explain
  - b. How can it be made better?
  - c. How would you prefer that self-test kits are distributed?
  - d. What impact has self-testing had in the communities that you serve?
  - e. Positive impact? Please explain
  - f. Negative impact? Please explain
2. What are the barriers and facilitators to self-testing
  - a. From the points of view of health care workers like yourself
  - b. From the community/clients' perspectives?
3. What are your views on the ANC, PLWHIV HIV self-testing model?
  - a. Will it increase uptake of HIV testing (compared to provider-delivered testing)?
    - i. What sorts of people are using this self-testing service?
4. What type of people are not using the service and why?

**C. Linkage to care**

1. What are your views on linkage to prevention and care services after self-testing? Do you think people will link as well, or better, or worse than if they were tested by providers?
  - a. Linkage to medical male circumcision for HIV negative males
  - b. Linkage to HIV treatment/care for those who test HIV positive
  - c. What is your role in linking people to care and preventive services?
  - d. What are the barriers to linking to care in this model?
  - e. What are the facilitators to linking to care?

**D. Social harms**

1. What are your views on social harms due to self-testing?
  - a. Do you think self-testing will have higher rates of social harms compared to provider-delivered testing? What sorts of harms do you think could result?
    - I. Forced testing?
    - II. Gender based violence?
  - b. Have you experienced any harm because of distributing kits to clients?
  - c. Are there any unfavourable outcomes because of people collecting kits for their partners in this community?

**E. Sustainability**

1. How can we sustain the giving of kits through ANC, PLWHIV, and Shops?
2. How can the community help in sustaining the different ways of distributing the kits?
3. What are the factors in the community that may cause these ways of distribution to be unsuccessful?
4. What do you think can be done to motivate the distributors?
5. What do you think are the demotivating factors?
6. In conclusion, are there any recommendations that you would like to share?

We have come to the end of our interview, thank you very much for your time.

